4.2 STUDY ENDPOINTS

4.2.1 PRIMARY ENDPOINTS

Primary endpoints include total therapeutic radiation dose delivered and DCE-CT profusion metrics at baseline, following first treatment, and 6 weeks after treatment. Profusion metrics include: KTrans (aka extraction-flow product), blood volume, and blood flow.

4.2.2 SECONDARY ENDPOINT

Patient demographic data will be combined with the primary endpoints to assess whether perfusion metrics differ depending on baseline demographics.

Demographic information (e.g., sex, age, race, etc.) will be combined with primary profusion endpoints.

5 STUDY ENROLLMENT AND WITHDRAWAL

5.1 PARTICIPANT INCLUSION CRITERIA

In order to be eligible to participate in this study, an individual must meet all of the following criteria:

1. Provision to sign and date the consent form
2. Stated willingness to comply with all study procedures and be available for the duration of the study
3. Be a Male or Female aged 18-100
4. Diagnosed with Liver HCC or metastases
5. Must be receiving or will plan to receive SBRT for Liver HCC or metastases

5.2 PARTICIPANT EXCLUSION CRITERIA

An individual who meets any of the following criteria will be excluded from participation in this study:

1. Allergy to iodine contrast
2. CT with contrast not offered as a Standard of Care
3. Pregnant women

5.3 STRATEGIES FOR RECRUITMENT AND RETENTION

This study will be open to all patients meeting eligibility criteria seen at the University of Colorado Cancer Center main campus in Aurora, CO.

Target sample size is 10 patients. In total, the Department of Radiation Oncology treats approximately 50 liver cancer patients with SBRT per year. Assuming an enrollment rate of 40% and a dropout rate of 25%, a conservative estimate is enrolling 10 patients in 12 months.

5.4 PARTICIPANT WITHDRAWAL OR TERMINATION

5.4.1 REASONS FOR WITHDRAWAL OR TERMINATION

Participants are free to withdraw from participation in the study at any time upon request. Study subjects may be prematurely terminated from the study for the following reasons:

- Physician, PI, and/or patient decides to discontinue radiation treatment
- Noncompliance with the study protocol

- Development of unrelated illness which compromises study participation
 - The subject withdraws consent (no further data collection or submission will be expected)
- Subjects may stop study participation for any reason without jeopardizing their relationship with the healthcare providers.

5.4.2 HANDLING OF PARTICIPANT WITHDRAWALS OR TERMINATION

Because this is a pilot study, where no clinical decisions will be made based on the DCE-CT, no effort will be made to follow withdrawn study participants or study participants that have completed the study.

5.5 PREMATURE TERMINATION OR SUSPENSION OF STUDY (STUDY STOPPING RULES)

This study may be temporarily suspended or prematurely terminated if there is sufficient reasonable cause. Written notification, documenting the reason for study suspension or termination, will be provided by the suspending or terminating party to the Lead PI ([name]). If the study is prematurely terminated or suspended, the PI will promptly inform the IRB and will provide the reason(s) for the termination or suspension.

Circumstances that may warrant termination or suspension include, but are not limited to:

- Determination of unexpected, significant, or unacceptable risk to participants.
- Insufficient compliance to protocol requirements.
- Data that are not sufficiently complete and/ or evaluable.
- Determination of futility.

Study may resume once concerns about safety, protocol compliance, and data quality are addressed and satisfy the sponsor, IRB and DSMC.

6 STUDY AGENT

6.1 STUDY AGENT(S) AND CONTROL DESCRIPTION

As described above, DCE-CT will be utilized to correlate perfusion imaging tumor changes with local control and normal tissue perfusion changes with normal tissue toxicities. All patients will undergo DCE-CT performed at the time of CT simulation, after the first fraction of SBRT, and 6 weeks after completion of SBRT (see schema). The DCE-CT scan performed at the time of CT simulation and subsequent scans will be performed in treatment position (which will be defined on an individual patient basis by the treating radiation oncologist). DCE-CT will be performed on

the Siemens AS open scanner within the University of Colorado Department of Radiation Oncology. Iodine contrast agent (50-100 mL) will be injected, per standard of care, at 3 mL per second and axial images centered at the tumor will be acquired.

7 STUDY PROCEDURES AND SCHEDULE

7.1 STUDY PROCEDURES/EVALUATIONS

1. Subject enrollment and initial visit with radiation oncologist

The subject will have a pre-treatment, standard of care work-up visit with the radiation oncologist. During this visit, the study team will explain the study to the patient and obtain informed consent. After consent has been obtained, the study team will assess if the subject meets study criteria and can be enrolled into the study.

2. Pre-treatment DCE-CT Imaging

During the initial CT simulation process, the pre-treatment perfusion imaging will be obtained using DCE-CT. The initial CT simulation process is used to create the radiation therapy treatment plan and is a part of SOC. At the end of the CT simulation session, additional DCE-CT imaging will be acquired.

3. Delivery of Radiation Therapy

Treatment will be performed on a linear accelerator with on-board imaging capabilities to align the subject to the same treatment position for every treatment session. Throughout treatment, the subject will have a weekly evaluation with the radiation oncologist to help manage any health problems that may arise.

Subjects will have DCE-CT imaging within six hours of receiving the first fraction of radiation therapy to assess the SBRT related changes to baseline perfusion characteristics.

4. Six week follow-up visit/Post-treatment DCE-CT Imaging

The subject will have a SOC six week follow-up visit with the radiation oncologist. During the consult, the radiation oncologist will assess any issues arising from radiation treatment. At this

consult, the subject will also undergo their final session of DCE-CT imaging to assess perfusion changes after completion of radiation therapy.

7.2 STUDY SCHEDULE

7.2.1 SCREENING

The screening process will begin once a patient is referred to radiation oncology for radiation therapy for the treatment of liver cancer. The patient will undergo a standard consultation with a radiation oncologist. The patient will be explained the risks and benefits of participation in the study. The patient will also be explained the study is completely voluntary. Patients will be informed of the study, explained the study purpose and asked to provide informed consent.

7.2.2 ENROLLMENT/BASELINE

- Verify inclusion/ exclusion criteria.
- Obtain Demographic information.
- Baseline clinical information (drinking status, medications, medical treatments including cancer treatments, cancer history)
- Obtain urine pregnancy test in women of childbearing potential.
- CT simulation for radiotherapy planning
- DCE-CT (performed at the time of CT simulation)

7.2.3 FOLLOW-UP

- Subjects will have DCE-CT imaging within six hours of receiving the first fraction of radiation therapy to assess the SBRT related changes to baseline perfusion characteristics
- DCE-CT imaging will be made at 6 weeks (+/- 1 week) after completion of SBRT.
- Record adverse events as reported by participant or observed by investigator if related to DCE-CT.
- Record participant's adherence to treatment program.

7.2.4 FINAL STUDY VISIT

- Record adverse events as reported by participant or observed by investigator if related to DCE-CT.

- Record participant's adherence to treatment program.

7.2.5 EARLY TERMINATION VISIT

No procedures will be performed.

7.2.6 UNSCHEDULED VISIT

No procedures will be performed.

7.2.7 SCHEDULE OF EVENTS TABLE

Study Visits					
	Screening	Baseline Visit	Mid-Treatment		6 weeks Follow-up
Visit Window	-28 Days to Day 0	Day 0- Prior to Treatment	Between 1 st and last treatment fractions		4-6 weeks post-treatment
Procedures					
Visit with Radiation Oncologist	X	X	X		X
Informed Consent	X				
DCE-CT imaging		X (R)	X (R)		X (R)
Adverse Events		X	X		X

Study Event	Suggested timeline	Procedure	SOC or Research
Screening	At time of initial consult with Radiation Oncology	Consultation with Radiation Oncologist	SOC
		Patient signs consent form	Research
Pre-Treatment DCE-CT imaging	Within 3 weeks prior to the initiation of radiation therapy	CT imaging for treatment planning	SOC
		DCE-CT imaging	Research
Delivery of Radiation Therapy	1-2 Weeks	Delivery of Radiation treatment of liver cancer	SOC
6 week follow-up visit	4-6 weeks after completion of radiation therapy	Appointment with radiation oncologist	SOC
		DCE-CT imaging	Research

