4 STUDY DESIGN AND ENDPOINTS

4.1 DESCRIPTION OF THE STUDY DESIGN

This is a pilot study designed to evaluate the feasibility of DCE-CT imaging for outcome assessment of radiation therapy for the treatment of liver cancer. Because this is a pilot study, no clinical decisions or interventions will deviate from standard of care.

Pre-treatment perfusion assessment will be performed before the start of SBRT. The first Post-treatment perfusion assessment will be within six hours after the end of the first fraction of SBRT. The final Post-treatment perfusion assessment will be six weeks after the end of SBRT (with an allowed time window of 4-8 weeks).

Step 1 (Enrollment & Screening):

Patients with liver cancer receiving stereotactic body radiation (SBRT) as part of their standard of care will be eligible for study enrollment. SBRT is similar to conventional, photon-based radiation therapy. SBRT differs from conventional radiation therapy by utilizing less treatment sessions, also call ‘a fraction’, and a higher radiation dose per treatment session. Typically, SBRT is 5 fractions, whereas conventional radiation therapy may have 10 to 30 fractions, depending on the total prescribed radiation dose. DCE-CT imaging will be added at three specific time points of the clinical workflow for the quantification of perfusion.

Step 2 (Pre-treatment perfusion assessment):

Subjects will have DCE-CT imaging before the initiation of radiation therapy. Under SOC, all patients receiving radiation therapy undergo a planning CT simulation session. This session of CT imaging produces the CT study that will be used to create the radiation treatment plan. Under this

study, an additional DCE-CT scan will be acquired to quantify a patient's baseline perfusion characteristics.

Step 3 (Initiation of Radiation Therapy and Post-treatment perfusion assessment):

Subjects will begin radiation therapy for treatment of liver cancer or metastases. Each individual treatment session, also known as a "fraction", will utilize on-board imaging to ensure localization of treatment to the patient's unique anatomy for each session. This is the SOC with no modifications to the radiation treatment characteristics. Subjects will have DCE-CT imaging within six hours of receiving the first fraction of radiation therapy to assess the SBRT related changes to baseline perfusion characteristics.

Step 4 (Completion of Radiation Therapy):

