10.3 ANALYSIS DATASETS

All participants who completed their baseline DCE-CT scan, had at least one radiation therapy treatment and one follow-up DCE-CT scan will be included in the analysis dataset to assess change in perfusion measurements from baseline to first follow-up. The analysis dataset for change in perfusion metrics at 6 weeks will include participants who completed their radiation treatment and have both baseline and 6-week DCE-CT scans.

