10.4.2 ANALYSIS OF THE PRIMARY EFFICACY ENDPOINT(S)

The primary endpoint of this study is change in profusion metrics from baseline to end of first radiation treatment and 6-weeks after treatment has ended. Additionally, total radiation dose delivered from SBRT will be captured and used as a surrogate measurement for treatment response.

Individual profusion metrics will be plotted as well as means with corresponding standard errors for the three time points. Change in profusion metrics from baseline versus radiation dose received will be plotted separately for the two follow-up DCE-CT scans. Correlation between change in profusion and total radiation dose received will be evaluated using Spearman's correlation coefficient.

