14.3 PROTOCOL DEVIATIONS

A protocol deviation is any noncompliance with the clinical trial protocol, GCP, or SOP requirements. The noncompliance may be either on the part of the participant, the investigator, or the study site staff. As a result of deviations, corrective actions are to be developed by the site and implemented promptly. These practices are consistent with ICH E6, sections:

- 4.5 Compliance with Protocol, sections 4.5.1, 4.5.2, and 4.5.3.
- 5.1 Quality Assurance and Quality Control, section 5.1.1.
- 5.20 Noncompliance, sections 5.20.1 and 5.20.2.

It is the responsibility of the study team to use continuous vigilance to identify and report deviations within 5 working days of identification of the protocol deviation, or within 5 working days of the scheduled protocol-required activity. All deviations must be addressed in study source documents, reported to CUCC DSMC. Protocol deviations must be sent to the local IRB per their guidelines. The site PI/ study staff is responsible for knowing and adhering to their IRB requirements. Further details about the handling of protocol deviations will be included in the - SOP and/or study procedures manual.

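### The visit table in 7.2.7 allows the early DCE-CT at any point up to the last fraction, the text requires it within six hours of fraction 1, and 10.3 has no rule to keep a late scan out of the early-change set

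*Combined protocol and SAP*

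**What the plan says.** The timing of the early scan is given in four places.

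- Section 4.1: "The first Post-treatment perfusion assessment will be within six hours after the end of the first fraction of SBRT".
- Section 7.1: "Subjects will have DCE-CT imaging within six hours of receiving the first fraction of radiation therapy to assess the SBRT related changes".
- Section 7.2.3 repeats it: "Subjects will have DCE-CT imaging within six hours of receiving the first fraction of radiation therapy".
- Section 7.2.7, first table: the DCE-CT is marked as a research procedure in the mid-treatment column, whose visit window is "Between 1 st and last treatment fractions".

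The second table in 7.2.7, which offers suggested timelines, lists the baseline and 6-week DCE-CT but has no row for the early one.

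On the analysis side, Section 10.4.2 defines the primary endpoint as "change in profusion metrics from baseline to end of first radiation treatment and 6-weeks after treatment has ended". Section 10.3 says that participants with a baseline scan, at least one radiation treatment and "one follow-up DCE-CT scan will be included in the analysis dataset to assess change in perfusion measurements from baseline to first follow-up". It attaches no timing condition to that scan. Section 14.3 states: "A protocol deviation is any noncompliance with the clinical trial protocol, GCP, or SOP requirements". It covers reporting and corrective action and does not say how data from a deviation are analysed.

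**The concern.** The table is the part of a protocol that coordinators tend to book from, and here neither table shows the six-hour limit. A scan on a later treatment day would look compliant to someone reading the first table and would be a deviation to someone reading the text.

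The early change is one of the two primary time points, and it is meant to describe perfusion just after a single fraction. If a scan taken after several fractions were summarised under that label, the value would answer a different question. The pilot is also intended to supply data for powering a larger study, so a mislabelled time point could carry forward.

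**Working it through.** **Inputs.** Course length 1 to 2 weeks and typically 5 fractions (4.1); range 3 to 8 sessions (2.2); target of 10 patients (5.3) and maximum of 15 (10.5). The plan gives no figure for scan timing compliance. Its one derived number, the maximum of 15, reproduces: 50 × 0.40 × (1 − 0.25) = 15.

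**Step 1: compare the windows.**

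| Source | Latest permitted time for the early scan |
|---|---|
| 4.1, 7.1, 7.2.3 | 6 hours after fraction 1 |
| 7.2.7, first table | up to the last fraction |
| 7.2.7, second table | scan not listed |
| 10.3 | no limit stated |

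A course of 1 to 2 weeks is at most 168 to 336 hours. The table window is therefore up to 168/6 = 28 to 336/6 = 56 times as wide as the text window. In fractions, the text allows one before the scan. The table allows up to 4 of 5 in a typical course, 2 of 3 in the shortest and 7 of 8 in the longest.

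**Step 2: sort scans by time.**
- Within six hours of fraction 1: meets the table and the text.
- After six hours, before fraction 2: meets the table and breaks the text, but still follows only one fraction.
- After fraction 2 or later: meets the table, breaks the text, and does not measure the early change as 10.4.2 defines it. The inclusion wording of 10.3 does not exclude it.

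**Step 3: weight of one late scan.** 1/10 = 10% of the early data; 1/15 = 6.7%.

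**Step 4: effect on the early Spearman coefficient.** Without ties, the largest possible shift comes from moving one patient's change from the lowest to the highest rank, and equals 6/(n+1): 6/11 = 0.55 at n = 10 and 6/16 = 0.38 at n = 15.

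For a typical shift, one patient's change was replaced in simulated data: 20,000 runs, bivariate normal, true correlation between dose and change of 0 or 0.5. The correlation between that patient's late and on-time values is an assumption, varied below.

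| Late vs on-time correlation | n = 10: median shift (95th percentile) | n = 15: median shift (95th percentile) |
|---|---|---|
| 0 (unrelated draw) | 0.06–0.07 (about 0.35) | 0.04–0.05 (about 0.23) |
| 0.5 to 0.8 | 0.024–0.048 (0.18–0.27) | 0.014–0.029 (0.11–0.17) |

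None of these runs includes a systematic effect of further fractions on perfusion, so the simulated figures illustrate scale and are not bounds.

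**The case against.** The strongest reply is that the table is coarser than the text, not opposed to it. The row is a visit window shared with the oncologist visit and adverse-event checks, and a wide window suits those: "Throughout treatment, the subject will have a weekly evaluation with the radiation oncologist". The six-hour window lies inside it, so staff who follow the text also satisfy the table. The rest of the protocol points one way. The synopsis, 4.2.1, 6.1, 8.1.1, 8.1.2, 8.2.2, 10.4.1 and 10.4.2 all tie this scan to the first treatment. The second table only suggests timelines, so its silence is weak evidence. The study is a descriptive pilot, and 10.2 plans no formal test.

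Most of this stands. The intent is clear, and harm arises only if someone schedules from the table. What remains is that the table gives the scan no other window, and that the clear intent is never turned into a rule for the analysis set.

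Three stronger readings are tempting and should not be drawn.
- That late scans would be analysed as early change. 10.4.2 points against it and 10.3 is silent on timing; only that they could be is supported.
- That 10.3 would admit a patient whose only follow-up scan is the 6-week one. Its words on inclusion could be stretched that far, but it concerns change to first follow-up, and 10.4.1 and 10.4.2 identify that as the scan after the first treatment.
- That the dose side of the correlation is compromised. 10.4.2 uses total dose received, which does not depend on when the scan was taken.

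**Conclusion.** The point holds as a minor internal inconsistency. The table window is wrong for this scan as written, and 10.3 lacks the one condition that would keep a scan taken after later fractions out of the early-change set. The consequence is confined to the early perfusion change of any patient scanned late. The per-scan effect is usually small; the figures in steps 3 and 4 depend on the assumed link between late and on-time values. The expected effect over the whole study cannot be stated, because the documents give no basis for how often a late scan would occur. The 6-week change is untouched.

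**What to change.** In 7.2.7, give the early DCE-CT its own window in the first table, within six hours after the end of fraction 1. Leave the visit and adverse-event window as it is. Add a row for this scan to the second table. Sections 4.1, 7.1 and 7.2.3 need no change on this point.

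In 10.3, name the follow-up scan for the early set as the post-fraction-1 scan taken before fraction 2, so that a scan after fraction 2 or later is not summarised as early change.

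The cost is one table cell, one table row and a sentence in 10.3, with no change to sample size, number of scans or patient burden. The downside is that each excluded scan takes 6.7% to 10% out of an already small early summary. Flagging scans that fall between six hours and fraction 2, and recording scan times, would be useful but is optional; the inconsistency can be resolved without either.

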7.4 PROHIBITED MEDICATIONS, TREATMENTS, AND PROCEDURES

There are no restrictions on concomitant medications, treatments (i.e. chemotherapy, hormonal, immunotherapy) and procedures while on study.

8 ASSESSMENT OF SAFETY

8.1 SPECIFICATION OF SAFETY PARAMETERS

8.1.1 DEFINITION OF ADVERSE EVENTS (AE)

Adverse event means any untoward medical occurrence associated with the use of an intervention in humans.

Because this is an imaging study, where no clinical decision will be altered, we will only record AEs that have to do with the research procedures. The three research procedures are the pre-treatment, post-first fraction, and post-treatment DCE-CT imaging.

8.1.2 DEFINITION OF SERIOUS ADVERSE EVENTS (SAE)

Serious adverse event or serious suspected adverse reaction. An AE or suspected adverse reaction is considered “serious” if, in the view of either the investigator or sponsor, it results in

any of the following outcomes: death, a life-threatening adverse event, inpatient hospitalization or prolongation of existing hospitalization, a persistent or significant incapacity or substantial disruption of the ability to conduct normal life functions, or a congenital anomaly/ birth defect. Important medical events that may not result in death, be life-threatening, or require hospitalization may be considered serious when, based upon appropriate medical judgment, they may jeopardize the patient or subject and may require medical or surgical intervention to prevent one of the outcomes listed in this definition. Examples of such medical events include allergic bronchospasm requiring intensive treatment in an emergency room or at home, blood dyscrasias or convulsions that do not result in inpatient hospitalization, or the development of drug dependency or drug abuse.

Because this is an imaging study, where no clinical decision will be altered, we will only record SAEs that have to do with the research procedures. The three research procedures are the pre-treatment, post-first fraction and post-treatment DCE-CT imaging.

8.1.3 DEFINITION OF UNANTICIPATED PROBLEMS (UAP)

This study will use the COMIRB definition of UAP. An unanticipated problem is any event or information that was unforeseen and indicates that the research procedures caused harm (including physical, psychological, economic, or social harm) to participants or others or indicates that participants or others are at increased risk of harm than was previously known or recognized.

